5.2 RESPONSE CRITERIA

RAI uptake and Tg level will be compared pre- and post-valproic acid treatment. The nuclear medicine radiologists using a planar technique will measure the RAI scan uptake. The post-valproic acid scan will then be compared side-to-side with the pre-valproic acid scan, using the planar technique, and will then be scored as "increased" or "unchanged" compared to zero/minimal (<1%) uptake seen on the pre-valproic acid scan. We will define 4 categories of response:

1. Complete response: increased RAI uptake on post-valproic acid therapy at week 10, AND a decrease in Tg level to less than 2 ng/ml (or a decrease in Tg-Ab level to less than 2.0 IU/ml) at 10 weeks AND disappearance of all lesions at 16 weeks.
2. Partial response: increased RAI uptake on post-valproic acid scan at week 10, OR a decreased Tg level (or a decrease in Tg-Ab level by more than 20%) at 10 weeks AND 30% decrease in target lesion at 16 weeks.
3. Stable disease: no change in RAI uptake AND Tg levels (or Tg-Ab level) AND no significant change of lesions 16 weeks.
4. Progressive disease: tumor mass increases OR Tg levels (or Tg-Ab levels) increases over 10 weeks OR at least 20% increase in target lesion at 16 weeks.

Target lesions will be evaluated according to the RECIST response criteria outlined below.

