5.2.1 Response Criteria RECIST 1.1

5.2.1.1 Evaluation of target lesions*

- Complete Response (CR): Disappearance of all target lesions. Any pathological lymph nodes (whether target or non-target) must have reduction in short axis to <10 mm.
- Partial Response (PR): At least a 30% decrease in the sum of diameters of target lesions taking as reference the baseline sum diameters.
- Progression (PD): At least a 20% increase in the sum of diameters of target lesions taking as reference the smallest sum on study (this includes the baseline sum if that is the smallest on study) or the appearance of one or more new lesions.

- Stable Disease (SD): Neither sufficient shrinkage to qualify for PR nor sufficient increase to qualify for PD taking as references the smallest sum diameters while on study.

* *All measurable lesions up to a maximum of 5 lesions (and a maximum of 2 lesions per organ) representative of all involved organs should be identified as **target lesions** and recorded and measured at baseline. Target lesions should be selected on the basis of their size (lesions with the longest diameter), be representative of all organs involved, and be suitable for accurate repetitive measurements (either by imaging techniques or clinically). A sum of the diameters (longest for non-nodal lesions, short axis for nodal lesions) for all target lesions will be calculated and reported as the baseline sum diameters. The baseline sum diameters will be used as reference to further characterize the objective tumor response of the measurable dimension of the disease.*

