6.2 SAMPLE SIZE AND POWER ANALYSIS

This is a phase II study aimed at measuring the impact of valproic acid on iodine uptake and on tumor response. Response will be defined as complete or partial response as outlined in section 5.2. The study uses a two-stage Simon optimal design with an interim analysis planned when 13 patients are evaluable for response. If no complete/partial responses are seen at that time the study will close to accrual. The study will proceed to stage II if at least one response is seen among the first 13 patients. At the end of study, if the cumulative number of responses among the 20 evaluable patients is 3 or more, valproic acid will be considered efficacious, while this will not be the case if 1-2 responses are noted. Under the null hypothesis of a true response rate that does not exceed 5% ($p_0=0.05$), the two-stage design will control type I error (α) to be no more than 7.4%, and when the true response rate is at least 25% ($p_1=0.25$), the study has at least 90% power ($\beta=0.10$). The probability of triggering early stopping is at least 51% if the true response rate is 5% or less, and less than 2.5% if the true response rate is 25% or more. If the accrual is stopped at the first stage due to futility, the upper bound of a 95% confidence interval for the response rate will be less than 25%. We will plan to enroll up to 25 patients with the expectation that 20 patients (80%) will be evaluable for response.

The stopping rule for Grade 3 toxicity is set at 15% as the acceptable toxicity rate because the study is designed to detect a treatment efficacy rate of 15% or higher. Therefore, if the acceptable toxicity rate is higher than the expected efficacy rate the study will be stopped.

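### The partial-response rule behind both decision points can be read in two ways, and sections 3.5.2 and 3.1 describe response differently again

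*Protocol*

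**What the plan says.** Section 6.2 makes section 5.2 the source of the decision count: "Response will be defined as complete or partial response as outlined in section 5.2". The first use of that count is futility: "If no complete/partial responses are seen at that time the study will close to accrual". The second is the final call, efficacious at 3 or more responses among 20 evaluable patients.

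Section 5.2 has four categories that mix radioiodine (RAI) uptake, thyroglobulin (Tg, or Tg antibody) and lesion size:

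- Partial response: "Partial response: increased RAI uptake on post-valproic acid scan at week 10, OR a decreased Tg level", then a parenthesis giving a Tg-Ab alternative, then "at 10 weeks AND 30% decrease in target lesion at 16 weeks".
- Stable disease: "Stable disease: no change in RAI uptake AND Tg levels (or Tg-Ab level) AND no significant change of lesions 16 weeks".
- Progressive disease: "Progressive disease: tumor mass increases OR Tg levels (or Tg-Ab levels) increases over 10 weeks", or a target-lesion increase of at least 20% at week 16.

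Section 5.2.1.1 gives the RECIST partial response for target lesions: "At least a 30% decrease in the sum of diameters of target lesions". The table in section 5.2.1.3 lets progression of target lesions, of non-target lesions, or by new lesions override any other finding.

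Two other places describe response differently. Section 3.5.2 (weeks 17-52) has Schedule 2 patients with either a RECIST response or a Tg fall since day 1 recorded as partial responders. Section 3.1 treats a Tg fall, RAI uptake or smaller tumour size, any one of them, as evidence of response.

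**The concern.** The partial-response line joins three conditions with one OR and one AND and does not group them:

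- **Broad reading:** increased uptake OR (Tg fall AND 30% shrinkage).
- **Narrow reading:** (increased uptake OR Tg fall) AND 30% shrinkage.

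The readings part for every patient with increased uptake and less than 30% shrinkage. This is no marginal group: raising uptake is a study objective (section 1.1.2), and Schedule 1 in section 3.5.1 is defined by increased uptake at week 10.

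Bracketing alone leaves a second gap. Any one progression criterion suffices, including a Tg rise, and 5.2 does not say which category prevails when a patient also meets partial response.

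At stake is the trial's conclusion. In a single-arm, open-label study with a threshold of 3 in 20, a grouping chosen after the scans have been read could decide the result.

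**Working it through.** **1. Reproduce the design.** Inputs from section 6.2: 13 patients at stage 1, stop at 0; 20 in total (7 more at stage 2), efficacious at 3 or more; p0 = 0.05, p1 = 0.25.

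P(stop) = (1 − p)^13

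P(efficacy) = P(Bin(20, p) ≥ 3) − (1 − p)^13 × P(Bin(7, p) ≥ 3)

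- p = 0.05: stop 0.5133; efficacy 0.0755 − 0.5133 × 0.0038 = 0.0736.
- p = 0.25: stop 0.0238; efficacy 0.9087 − 0.0238 × 0.2436 = 0.9030.

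These match the stated figures: alpha at most 7.4%, power at least 90%, early stopping at least 51% and below 2.5%.

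**2. Apply both readings to every combination.** Take uptake (increased, unchanged) × Tg (down, same, up) × target lesions (at least 30% smaller, neither, at least 20% larger): 2 × 3 × 3 = 18 profiles.

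| | Broad | Narrow |
|---|---|---|
| Profiles meeting partial response | 10 | 4 |
| Meeting partial response and progression | 5 | 1 |
| Meeting none of partial response, stable, progression | 2 | 4 |

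Six profiles (10 − 4) change status through grouping alone. All six have increased uptake without 30% shrinkage. Complete responders satisfy both readings.

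Of the five broad-reading overlaps with progression, three include target-lesion growth and two rest on a Tg rise alone. The single narrow-reading overlap (uptake up, lesions at least 30% smaller, Tg up) also rests on a Tg rise alone. The grid leaves out growth outside the target lesions. A Tg fall with target shrinkage and increased tumour mass elsewhere would meet both categories on either reading, so these overlap counts are minima.

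**3. Same patients, opposite result.** Suppose three patients have increased uptake and less than 30% shrinkage, at least one is among the first 13, none is overridden by progression, and nobody else responds. Broad reading: the trial passes stage 1 and ends with 3 responses, efficacious. Narrow reading: 0 of 13, accrual closes. No assumed rate is needed.

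**4. Illustrative size.** The protocol gives no rate for uptake, Tg fall or shrinkage, so these are assumptions. Let the true rate be 5% on the narrow reading, and let uptake alone, net of any override by progression, add d points on the broad one. The formulas in step 1 give:

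| d | Broad rate | P(stop at 13) | P(efficacy) |
|---|---|---|---|
| 0 (same as narrow) | 5% | 51.3% | 7.4% |
| 5 | 10% | 25.4% | 31.7% |
| 10 | 15% | 12.1% | 58.6% |
| 20 | 25% | 2.4% | 90.3% |

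Conversely, if 25% is the broad rate and 80%, 60% or 40% of those patients also meet the narrow rule, the narrow rates are 20%, 15% and 10%, and power is 78.6%, 58.6% or 31.7%.

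**5. Sections 3.5.2 and 3.1.** Schedule 2 patients have no increased uptake, so both readings of 5.2 reduce to Tg fall AND 30% shrinkage. Section 3.5.2 accepts a Tg fall, or a RECIST response, by itself. Section 3.1 accepts any one of the three signs. Neither reading of 5.2 reproduces these rules.

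**The case against.** **The text favours the broad reading.** This stands. Stable disease requires unchanged uptake, so on the narrow reading a patient with increased uptake and no other change fits no category. Sections 1.2, 3.1 and 7.4 treat uptake as evidence in its own right, and 6.2 describes the aim as "measuring the impact of valproic acid on iodine uptake and on tumor response". Nor does the RECIST partial response count for the narrow reading, since it defines only the lesion component. A reader might infer that the two readings are evenly supported, and they are not. Still, a lean is not a rule for a count with a threshold of 3. The study schema in Appendix 1 is not in the supplied text and could bear on this.

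**Progression does have precedence somewhere.** This stands in part. A reader might infer that the protocol has no precedence rule at all, but the table in 5.2.1.3 makes progression override for RECIST lesions. Nothing says that the table governs the composite categories of 5.2, and it contains no uptake, Tg or Tg-Ab row, so it cannot set a partial response against a marker rise. Section 3.9.1 lists progression as a reason for leaving protocol therapy but does not classify response for 6.2.

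**Such detail belongs in the SAP.** A tie-break might be there. The grouping is different: the protocol itself writes the rule and binds the stopping decision to it.

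**The magnitude is assumed.** True. The largest contrast, 90.3% against 7.4%, sets the two rates at p1 and p0 and so only restates the design's power and alpha. It marks the end of a range, not an expected effect.

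**Section 6.1 reports types of response with confidence intervals.** That helps a reader see what a positive count rests on, but it does not repair the stopping rule.

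**Conclusion.** The concern holds and should be fixed before response data are reviewed. The rule that feeds both decisions has two grammatical readings, which disagree for every patient with increased uptake and less than 30% shrinkage, and sections 3.5.2 and 3.1 fit neither. Precedence is open chiefly where a partial response coincides with a Tg or Tg-Ab rise. For lesion growth, the open question is whether the RECIST table applies to the 5.2 categories.

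A reader might infer that type I error is inflated. The document does not support that: 7.4% and 90% are right for any one fixed definition. The defect is that p0 = 5% and p1 = 25% are not attached to one.

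The disagreement over which patients count rests on the text alone. Its effect on the decision probabilities depends on assumed rates: it is nil if uptake alone adds no responders, and rises to the figures in the table as it adds 5 to 20 points to a narrow rate of 5%.

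**What to change.** Before any response data are reviewed:

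1. Bracket the partial-response rule in 5.2 to one reading, and add a sentence in 6.2 confirming that p0 and p1 refer to it.
2. State whether the progression override in 5.2.1.3 applies to the four categories of 5.2, and which category prevails when a partial response coincides with a Tg or Tg-Ab rise.
3. Reconcile the partial-response wording in 3.5.2 and the response wording in 3.1 with 5.2.

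The choice of reading, and any rule on continuing treatment, remain with the sponsor.

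The cost is a wording amendment to four sections (5.2, 6.2, 3.5.2 and 3.1), with no added patients or visits. Each choice has a price: the narrow reading may make p1 = 25% harder to support, and the broad one lets a positive result rest on uptake alone.

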 - CBC with differential, platelets, BUN, creatinine, total protein, total bilirubin, ALT, AST, ALKP, amylase, ammonia, albumin and b-HCG (if applicable).
 - Toxicity assessment and review of diary
- Week 16:
 - Physical exam including ECOG status
 - CBC with differential, platelets, BUN, creatinine, total protein, total bilirubin, ALT, AST, ALKP, amylase, ammonia, albumin and b-HCG (if applicable).
 - Tg, TSH
 - Toxicity assessment and review of diary
 - Ultrasound of the neck and mediastinum
 - MRI or CT of the neck and chest
 - FDG-PET scan
 - Health Related Quality of Life HRQOL) form completion
- Weeks 17-52
 - Patients who show a response by RECIST criteria or have a decreased thyroglobulin level from Day 1 of the treatment (registered as a partial response to the treatment) will continue on valproic acid at their current dose for a total of 52 weeks.

- Stop valproic acid if no response
- Sixteen weeks or 4 months is significant amount of time to measure response to treatment and therefore, if there is a response, a patient's thyroglobulin levels should have decreased by then, as well as, by RECIST criteria.
- Patients who show no response, patients will stop valproic acid treatment and continue with routine follow up.

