6 STATISTICAL CONSIDERATIONS

6.1 RATES AND TYPES OF RESPONSES

Rates and types of responses will be determined and presented with 95% confidence intervals. Patient characteristics (demographic and clinical) will be tabulated. Overall survival will be summarized using Kaplan-Meier curves. Toxicities will be tabulated by grade and organ system. Summary responses to the quality of life instrument at selected time points will be tabulated; to aid in the interpretation of temporal changes in quality of life items, change scores will be evaluated using the Wilcoxon signed rank test or McNemar's test as appropriate.

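### The four response categories in section 5.2 leave ordinary outcomes unclassified, and sections 3.5.2 and 5.2.1 classify those same patients as responders

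*Protocol*

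**What the plan says.** Protocol section 6.2 sets the endpoint: "Response will be defined as complete or partial response as outlined in section 5.2". The study stops if none of the first 13 evaluable patients responds, and valproic acid is called efficacious if at least 3 of 20 respond. Section 6.1 adds: "Rates and types of responses will be determined and presented with 95% confidence intervals".

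Section 5.2 gives four categories.

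- Complete response (CR): "Complete response: increased RAI uptake on post-valproic acid therapy at week 10, AND a decrease in Tg level to less than 2 ng/ml", together with disappearance of all lesions at week 16.
- Partial response (PR): "Partial response: increased RAI uptake on post-valproic acid scan at week 10, OR a decreased Tg level", with a parallel condition for Tg antibodies, then "at 10 weeks AND 30% decrease in target lesion at 16 weeks". The OR and the AND are not bracketed.
- Stable disease (SD): "Stable disease: no change in RAI uptake AND Tg levels (or Tg-Ab level) AND no significant change of lesions 16 weeks".
- Progressive disease (PD): "Progressive disease: tumor mass increases OR Tg levels (or Tg-Ab levels) increases over 10 weeks OR at least 20% increase in target lesion".

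Two other places also define response. Section 5.2.1, a subsection of 5.2, gives RECIST 1.1, where a 30% decrease in the sum of target diameters is a partial response with no condition on Tg or uptake. Section 3.5.2 covers patients without increased uptake at week 10. Those who continue drug after week 16 are: "Patients who show a response by RECIST criteria or have a decreased thyroglobulin level from Day 1 of the treatment". A parenthesis straight after the Tg limb says that this is recorded as a partial response.

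**The concern.** A set of response categories should give every patient exactly one class. Here stable disease requires uptake, Tg and lesions all to be unchanged, so it cannot take the patients left over from the other three. A patient whose lesions shrink without a marker change, or whose Tg falls while the lesions stay the same, has no place in the list.

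This would be a tabulation problem only if no other text classified such patients. But 3.5.2 and 5.2.1 do classify them, as responders. The decision rule works on very small counts, so it matters which text the person assigning the response follows. The error could go either way: a tumor-size responder could be lost, or Tg-only falls could be added.

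**Working it through.** **Inputs.** Category definitions from 5.2 and 5.2.1; the continuation text from 3.5.2; the decision rule and its stated properties from 6.2.

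**1. The design reproduces.** With 13 patients in stage 1, 7 more in stage 2, at least 1 response needed to continue and at least 3 of 20 to succeed:

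P(success) = P(X20 ≥ 3) − P(X13 = 0) × P(X7 ≥ 3), where Xn is binomial(n, p).

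The subtracted term removes trials that would have reached 3 responses but stopped at stage 1. At p = 0.05: P(X20 ≥ 3) = 0.0755, P(X13 = 0) = 0.95^13 = 0.5133 and P(X7 ≥ 3) = 0.0038. The result is 0.0755 − 0.5133 × 0.0038 = 0.0736, as stated (at most 7.4%). At p = 0.25 the power is 0.903 (stated at least 90%). Early stopping has probability 0.513 at 5% and 0.75^13 = 0.024 at 25%, also as stated.

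**2. Two patients, both with uptake unchanged.**

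| Test | (a) at least 30% shrinkage, Tg unchanged | (b) Tg lower, lesions stable |
|---|---|---|
| CR in 5.2 | No: uptake and Tg conditions not met | No: lesions remain |
| PR in 5.2, read as (uptake OR Tg) AND 30% | No: no marker change | No: no 30% decrease |
| PR in 5.2, read as uptake OR (Tg AND 30%) | No: no marker change | No: no 30% decrease |
| SD in 5.2 | No: lesions changed | No: Tg changed |
| PD in 5.2 | No | No |
| RECIST in 5.2.1, target lesions | PR, or CR if all lesions vanish | SD |
| 3.5.2 | Response, imaging limb | Response, recorded as PR |

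**3. Extent of the gap.** Cross uptake (increased, unchanged) with Tg (below 2, decreased, unchanged, increased) and lesions (gone, 30% smaller, stable, grown by less than 20%, grown by at least 20%): 2 × 4 × 5 = 40 combinations. Growth of less than 20% is taken as PD, because 5.2 counts any increase in tumor mass.

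- Read as uptake OR (Tg AND 30%), 4 are unclassified. All have unchanged uptake: Tg below 2 with stable lesions; Tg decreased with stable lesions; Tg unchanged with lesions gone; Tg unchanged with 30% shrinkage.
- Read as (uptake OR Tg) AND 30%, 7 are unclassified: the same 4, plus increased uptake and stable lesions with Tg below 2, decreased or unchanged.

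Four are therefore common to both readings. These are counts of combinations, not of patients.

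**4. Overlap.** Some combinations are both PR and PD. Under either reading, increased uptake with a Tg rise and 30% shrinkage (or disappearance) meets both. A fix therefore needs an order of precedence as well as a residual class.

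**5. Effect on the decision.** One extra response turns 0 of 13 into 1 of 13, or 2 of 20 into 3 of 20; two turn 1 of 20 into 3 of 20. To illustrate, suppose that counting Tg-only falls raised the null response rate. The raised rates are assumptions; the protocol gives no figure.

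| Null rate when Tg-only falls are counted | P(declare efficacious) |
|---|---|
| 5% (no addition) | 7.4% |
| 10% | 31.7% |
| 15% | 58.6% |

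**The case against.** The strongest reply is that 6.2 names a single source for the endpoint, section 5.2, while 3.5.2 only decides who stays on drug. For a yes/no endpoint, a patient who meets neither CR nor PR is a non-responder, so the missing class alone does not change the count. This stands. A reader might infer that the coverage gap by itself makes the responder count undefined; the documents do not support that. What remains is that 3.5.2 uses the language of endpoint registration, and that 5.2.1 lies inside the section 6.2 cites.

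A reader might also infer that 3.5.2 records both patients as partial responders. The parenthesis follows the Tg limb, so it is safely read only for (b). Nor is it established that (a) goes uncounted: 5.2 ends by sending target lesions to RECIST, so the status of (a) is ambiguous.

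Requiring a marker change as well as shrinkage may be deliberate. Objective 1.1.1 joins Tg and tumor size with an and, although section 1.2 uses and/or. This also stands, and it is why the fix asks for a decision and does not impose one.

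Finally, it is tempting to say that about half of patients would be unclassified, taking Tg noise as symmetric. That treats every numerical movement in Tg as a change and applies only where uptake and lesions are unchanged. The protocol gives no figure behind it, and it is not relied on here.

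**Conclusion.** The point holds in limited form. Section 5.2 has no residual class, and 4 of 40 combinations are unclassified under either reading of the partial-response line (7 under one of them). For the 6.2 endpoint, (b) is a non-responder although 3.5.2 records a partial response, and the status of (a) depends on whether 5.2.1 is read as part of the definition. At 1 in 13 and 3 in 20, one or two such patients can decide the trial.

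The classification gap needs no assumption about patients. The rise from 7.4% to 31.7% or 58.6% rests on assumed null rates and on staff counting the 3.5.2 registrations despite 6.2. A reader might take those figures as the trial's true type I error; they are not. Under 5.2 as 6.2 cites it, Tg-only falls with unchanged uptake are not responses.

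A reader might also object that vanished lesions with Tg below 2 and unchanged uptake cannot be a complete response. That is true, but the patient meets PR, so the combined count is unaffected.

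**What to change.** 1. In 5.2, define stable disease as not CR, PR or PD, the residual logic that 5.2.1.1 already uses for target lesions.
2. State once, for the 6.2 endpoint, whether RECIST shrinkage without a marker change counts as a response.
3. Give an order of precedence between PR and the PD rule, under which a Tg increase is progression, so that no patient is both. Simply declaring shrinkage a PR whatever happens to Tg would not do: unchanged uptake, 30% shrinkage and a Tg rise is PD only today, and would become PR and PD.
4. If shrinkage alone is to count, confirm that the 5% null rate still applies to the wider endpoint.
5. In 3.5.2, replace the parenthesis about partial response with a reference to 5.2, so that endpoint registration is separate from the decision to continue drug. The passages on continuation must be reconciled; no continuation rule is proposed here.

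The cost is protocol wording, with no new assessments. These changes do not settle the unbracketed OR/AND, the missing size for a Tg change, or the different Tg time points in 5.2 (week 10) and 3.5.2 (from Day 1, in the week 16 decision); the same edit is the natural place to address them.

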3.9 CRITERIA FOR REMOVAL FROM PROTOCOL THERAPY AND OFF STUDY CRITERIA

3.9.1 Criteria for removal from protocol therapy

- Patient request
- PI discretion, if the PI feels it is not in the best interest of the patient to remain on treatment
- Liver Dysfunction (enzyme levels above 1.5 times ULN)
- Platelet < 50,000
- Ammonia levels > 65 mol/l
- Progressive disease
- Pregnancy
- Pancreatitis (amylase level above 1.5 ULN)
- Alcohol consumption
- Other unacceptable toxicities as determined by the PI

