5.2.1.2 Evaluation of non-target lesions **

- Complete Response (CR): Disappearance of all non-target lesions and normalization of tumor marker level. All lymph nodes must be non-pathological in size (<10mm short axis).
- Non-CR/Non-PD: Persistence of one or more non-target lesions and/or maintenance of tumour marker level above the normal limits.
- Progression (PD): Appearance of one or more new lesions. Unequivocal progression of existing non-target lesions

** All other lesions (or sites of disease), including pathological lymph nodes should be identified as **non-target lesions** and should also be recorded at baseline. Measurements are not required, and these lesions should be followed as “present”, “absent”, or in rare cases “unequivocal progression.”

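### The unsized tumor-mass condition for progressive disease in section 5.2 conflicts with the protocol's own 20% threshold, its stable-disease line and RECIST 1.1 in section 5.2.1

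*Protocol*

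**What the plan says.** Section 5.2 of the protocol sets four response categories. The fourth reads "Progressive disease: tumor mass increases OR Tg levels (or Tg-Ab levels) increases over 10 weeks OR at least 20% increase in target lesion", with the last condition timed at week 16 ("at least 20% increase in target lesion at 16 weeks"). The third, stable disease, requires among other things "no significant change of lesions 16 weeks". The section closes with "Target lesions will be evaluated according to the RECIST response criteria outlined below".

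Section 5.2.1.1 then gives the RECIST 1.1 rules for target lesions. Progression is "At least a 20% increase in the sum of diameters of target lesions taking as reference the smallest sum on study", or a new lesion. Stable disease is "Neither sufficient shrinkage to qualify for PR nor sufficient increase to qualify for PD". For non-target disease, section 5.2.1.2 counts a new lesion or "Unequivocal progression of existing non-target lesions".

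Two other sections use these categories. Section 6.1 reports how often each type of response occurs, with 95% confidence intervals. Section 3.9.1 lists "Progressive disease" among the reasons for removal from protocol therapy.

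**The concern.** The conditions for progressive disease are joined by OR, so the loosest one sets the boundary. The tumor-mass condition is the loosest lesion condition possible: any increase satisfies it. A patient whose lesions grow by 5% or 10% is then progressive under the fourth category of section 5.2. The same patient may be stable under the third category and is stable under section 5.2.1.1.

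Two things are at stake. First, the stable/progressive split in the section 6.1 tables would depend on measurement noise or on which sentence the assessor applies. Second, progressive disease is a removal criterion, so a patient's status under section 3.9.1 could depend on the same choice. Under section 3.5.2, a Schedule 2 patient whose thyroglobulin has fallen by week 16 continues to week 52. If that patient's lesions have grown by 5%, the literal tumor-mass condition also makes the patient progressive under section 3.9.1.

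**Working it through.** **1. The rules side by side.** Take an illustrative patient whose summed target diameters go from 50 mm to 55 mm at week 16, with no new lesion. The change is (55 − 50)/50 = 10%.

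| Rule | Result |
|---|---|
| 5.2 progressive, tumor-mass condition, read literally | Progressive |
| 5.2 progressive, 20% condition | Not met (10% < 20%) |
| 5.2 stable, lesion part | Met if 10% is not significant; no size is given |
| 5.2.1.1 target lesions | Stable |

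**2. Is the 20% condition redundant?** At the same assessment, target growth of 20% or more is also an increase in tumor mass, so the 20% condition adds no one. If the ten-week qualifier governs the tumor-mass condition as well as thyroglobulin, the conditions apply at different times and strict redundancy disappears: a lesion unchanged at week 10 and up 25% at week 16 is caught only by the 20% condition. On that reading, however, the week-10 visit in section 3.3 lists a physical examination and a Thyrogen scan but no CT, MRI or ultrasound for lesion measurement. Those come at week 16 (Schedule 2) or week 17 (Schedule 1) in section 3.5.

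**3. How often would unchanged lesions be called progressive?** The protocol gives no measurement error, so every SD here is an assumption. Let the observed relative change in summed diameters be normal with mean 0 and standard deviation SD.

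- Any increase: P(Z > 0) = 0.50, whatever the SD.
- Increase of at least 20%: P(Z > 0.20/SD).
  - SD 8%: P(Z > 2.50) = 0.0062
  - SD 10%: P(Z > 2.00) = 0.0228
  - SD 15%: P(Z > 1.33) = 0.0912

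With readings rounded to whole millimetres (simulation; 1 to 5 lesions of 10 to 40 mm, reading SD 0.5 to 2 mm), repeat sums tie in 6% to 49% of cases. Any increase then occurs in 26% to 47%, and an increase of at least 20% in 0% to about 9%.

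If a reader disregards changes under 5%, P(Z > 0.05/SD) runs from 5% at SD 3% to 40% at SD 20%.

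For scale, in 20 evaluable patients with no true lesion change, 25% to 50% is 5 to 10 patients. The 20% rule gives 20 × 0.0062 = 0.1, 20 × 0.0228 = 0.5 or 20 × 0.0912 = 1.8.

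**4. Does the design in section 6.2 change?** With 13 patients in stage 1, 20 in total and success at 3 or more responses:

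- Early stopping: 0.95^13 = 51.3% at a 5% response rate; 0.75^13 = 2.4% at 25%.
- P(success) = Σ over x = 1 to 13 of P(Bin(13, p) = x) × P(Bin(7, p) ≥ 3 − x) = 7.36% at p = 0.05 and 90.3% at p = 0.25.

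These reproduce the stated figures (at most 7.4%, at least 90%, at least 51%, less than 2.5%). They depend only on the rate of complete or partial response, not on how progressive disease is defined.

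**5. What remains after the lesion part is aligned?** The thyroglobulin condition is also unsized. With unchanged thyroglobulin and symmetric assay error it labels about 50% progressive by itself. Assuming independence, the two unsized conditions together give 1 − 0.5 × 0.5 = 75%. With the 20% lesion rule instead, 1 − 0.5 × (1 − 0.0062) = 50.3% at SD 8%, 51.1% at SD 10% and 54.6% at SD 15%.

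**The case against.** The strongest defence is the sentence that closes section 5.2, which sends target lesions to RECIST. On that view 5% or 10% target growth is meant to be stable, and the tumor-mass wording may refer to disease outside the target lesions. This shows the likely intent and defeats any claim that the 20% condition can never add a patient. It does not rescue the wording: section 5.2.1.2 asks for unequivocal progression or a new lesion in non-target disease, not any increase.

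A reader might infer that the protocol will call half of unchanged patients progressive. The documents do not support that as a fact. It needs every positive difference to count, symmetric error and no ties, and the stable-disease line suggests some tolerance.

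A reader might also infer that a week-10 lesion assessment is impossible. That is too strong. Section 1.3 mentions imaging for response after 10 weeks (which may mean only the Thyrogen scan), section 3.7.1 plans week-10 biopsies of accessible target lesions under ultrasound or CT guidance, and the footnote to section 5.2.1.1 allows clinical measurement. What stands is that section 3.3 schedules no anatomical imaging for measurement at that visit.

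Finally, the effect on treatment is limited. Under section 3.5, Schedule 1 patients stop valproic acid at the end of week 17, and Schedule 2 patients without response stop after the week-16 evaluation, whether stable or progressive. The label matters for growth detected clinically before week 16 and for patients who continue because thyroglobulin has fallen.

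**Conclusion.** The point holds as a conflict between stated rules, not as missing detail. Section 5.2 has an unsized tumor-mass condition that disagrees with the 20% condition beside it, with the stable-disease line above it and with section 5.2.1. Redundancy of the 20% threshold follows only when both conditions are read literally at the same assessment.

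If any positive difference counts, roughly 25% to 50% of patients with truly unchanged lesions would be labelled progressive, against 0.6% to 9.1% under a 20% rule for assumed SDs of 8% to 15%. If small changes are disregarded, the first figure is lower. All of these rest on assumed error, since the protocol gives none.

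The consequence is a stable/progressive split that is not reproducible, and an unclear status under section 3.9.1 for some patients. It would be wrong to conclude that the Simon design fails: its stated type I error, power and sample size reproduce and are unaffected.

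**What to change.** For response classification, remove the unsized tumor-mass condition from the progressive-disease line in section 5.2. Let the lesion part be the section 5.2.1 criteria that the protocol already adopts: growth of 20% or more in the summed target diameters from the smallest sum on study, a new lesion, or unequivocal progression of non-target disease.

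Sections 5.2, 5.2.1, 3.5.2 and 3.9.1 must also be reconciled so that progressive disease has one meaning wherever it bears on treatment. How continuation and removal should work is for the study team to decide.

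The classification change costs one line and no new assessment. Target growth below 20%, without a new lesion or unequivocal non-target progression, no longer counts as lesion progression, which is what section 5.2.1 already says. The thyroglobulin condition in the same line needs its own correction.
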